5.2.2 CGI-S

The CGI-S is a clinician-rated, 7-point scale that is designed to rate the severity of the subject's illness, in this study irritability associated with ASD, at the time of assessment, making use of the clinician's judgment and past experience with subjects who have the same disorder (Guy 1976). The CGI-S of irritability will be administered at Screening and Baseline, and at all visits from Week 1 through Week 6. The possible scores are 1=normal, not ill, 2=minimally ill, 3=mildly ill, 4=moderately ill, 5=markedly ill, 6=severely ill, 7=among the most extremely ill.

Missing CGI-S of irritability scores will not be imputed.

5.2.3 CGI-I

The CGI-I is a clinician-rated, 7-point scale that is designed to assess how much the subject's illness, in this study irritability associated with ASD, has improved or worsened relative to a baseline state at the beginning of the intervention, i.e., status at Baseline (Guy 1976). The CGI-I of irritability will be administered at all visits from Week 1 through Week 6. The possible scores are 1=very much improved, 2=much improved, 3=minimally improved, 4=no change, 5=minimally worse, 6=much worse, 7=very much worse.

Missing CGI-I of irritability scores will not be imputed.

5.2.4 Repetitive Behavior Scale-Revised (RBS-R)

The RBS-R (Lam and Aman 2007) is a 43-item parent/caregiver-facing questionnaire. Items are conceptually grouped into six subscales:

- stereotyped behavior (movements with no obvious purpose that are repeated in a similar manner): 6 items
- self-injurious behavior (actions that cause or have the potential to cause redness, bruising, or other injury to the body): 8 items

- compulsive behavior (behavior that is repeated and performed according to a rule or involves things being done "just so"): 8 items
- ritualistic behavior (performing activities of daily living in a similar manner): 6 items
- sameness behavior (resistance to change, insisting that things stay the same): 11 items
- restricted behavior (limited range of focus, interest, or activity): 4 items

Items are rated on a 4-point Likert scale ranging from (0) "behavior does not occur" to (3) "behavior occurs and is a severe problem", and raters are asked to refer to the previous month when completing the scale. The total RBS-R score is calculated as the sum of all subscale scores. Missing RBS-R item scores will not be imputed.

The RBS-R will be administered at Screening and Baseline, and at the Week 3 and Week 6 visits.

5.2.5 Vineland Adaptive Behavior Scales-Socialization (VABS-Socialization)

The VABS is a parent/caregiver-facing measure of adaptive behavior, organized into three domains: communication, daily living skills, and socialization (Sparrow et al. 2016). Only the socialization domain will be used in this study.

The socialization domain is a 112 item questionnaire with 3 subdomains: interpersonal relationships, play and leisure, and coping skills. Items are rated in a 0,1,2 scale. 2 (behavior is usually performed), 1 (behavior is sometimes performed), 0 (behavior is never performed). Missing VABS-Socialization item scores will not be imputed.

The VABS-Socialization will be administered at Baseline and at the Week 3 and Week 6 visits.

5.2.6 Caregiver Strain Questionnaire

The Caregiver Strain Questionnaire (CGSQ) (Brannan et al. 1997) is a 21-item parent/caregiver-facing questionnaire of self-reported strain experienced in the past 6 weeks (Screening visit), or since last visit (all other visits) by parents/caregivers and families of children and adolescents with serious emotional and behavioral disorders. Responses are on a 5-point Likert scale ranging from (1) "not at all a problem" to (5) "very much a problem".

The following areas of strain are included:

- disruption of family life and relationships
- demands on time
- negative mental and physical health effects for any member
- financial strain

- sacrifice
- disruption of social/community life
- worry and guilt
- fatigue and strain
- embarrassment
- child-caregiver relationship

The total score is sum of the following three subscale scores:

- objective strain (mean of items 1-11),
- subjective internalized strain (mean of items 12, 16-18, 20-21), and
- subjective externalized strain (mean of items 13, 14 reversed, 15, 19).

The CGSQ will be administered at Screening and Baseline, and at the Week 2, Week 4, and Week 6 visits.

Missing CGSQ item scores will not be imputed.

5.2.7 Columbia-Suicide Severity Rating Scale (C-SSRS)

The C-SSRS will be administered at Screening and Baseline, at all visits from Week 1 through Week 6, and at unscheduled visits. The C-SSRS monitors changes in suicidal thinking and behavior over time, in order to determine risk (Posner et al. 2011). Four constructs are measured: the severity of ideation, the intensity of ideation, behavior, and lethality. The Baseline/Screening version (Lifetime and past 6 months) will be administered at Screening, and the Since Last Visit version will be administered at subsequent visits including Baseline visit.

There are 5 questions about suicidal ideation, representing 5 types of suicidal ideation: wish to be dead; non-specific active suicidal thoughts; active suicidal ideation with any methods (not plan) without intent to act; active suicidal ideation with some intent to act, without specific plan; active suicidal ideation with specific plan and intent. If a subject/caregiver answers "yes" to any of these 5 questions, this subject will be counted as having suicidal ideation.

There are 5 questions about suicidal behavior, representing 5 types of suicidal behavior: preparatory acts or behavior; aborted attempt; interrupted attempt; actual attempt; suicide. If a subject answers "yes" to any of these 5 questions, this subject/caregiver will be counted as having suicidal behavior.

Missing C-SSRS item scores will not be imputed.

5.2.8 Extrapyramidal Symptom Rating Scale-Abbreviated (ESRS-A)

The ESRS (Chouinard and Margolese 2005) was developed to assess drug induced movement disorders such as parkinsonism, akathisia, dystonia, and tardive dyskinesia with established reliability, validity, and sensitivity. It consists of a questionnaire of parkinsonian symptoms, physician examination of parkinsonism, dyskinetic movements, and global impression of tardive dyskinesia. The ESRS-A, an accepted modified form of the original ESRS, will be used during the study to monitor for any worsening in extrapyramidal symptoms or signs at scheduled and unscheduled visits.

ESRS-A consists of 4 subscales and 4 clinical global impression movement severity scales of Parkinsonism, dyskinesia, dystonia, and akathisia. The Parkinsonism subscale consists of 10 items, the dyskinesia subscale consists of 6 items, the dystonia subscale consists of 6 items, and the akathisia subscale consists of 2 items. Each item is scored on a 6-point scale (0=absent, 1=minimal, 2=mild, 3=moderate, 4=severe, 5=extreme). The ESRS-A total score is the sum of the 24 item scores with a possible range of 0 to 120. Higher scores denote more severe symptoms of a movement disorder.

Missing ESRS-A item scores of the 4 subscales will not be imputed. The ESRS-A total score will be missing if any item score of the 4 subscales is missing.

Each clinical global impression movement severity scale of Parkinsonism, dyskinesia, dystonia, and akathisia is a single-item 6-point scale (0=absent, 1=minimal, 2=mild, 3=moderate, 4=severe, 5=extreme). The score ranges from 0 to 5, with higher scores indicating more severe movement disorders. Missing clinical global impression movement severity score will not be imputed.

The ESRS-A will be administered at Screening, Baseline, Week 1, Week 2, Week 3, Week 4, Week 5, and Week 6 visits; and at unscheduled visits. The ESRS-A will only be conducted at clinic visits and not at remote visits.

5.3 Analysis Visits

5.3.1 Study Day

Study Day 1 is defined as the first dose date of study drug (pimavanserin or placebo). If the date of assessment occurs on or after the first dose date, then study day will be calculated as (date of assessment – date of first dose) + 1. If the date of assessment occurs prior to the first dose date, then study day will be calculated as (date of assessment – date of first dose).

5.3.2 Analysis Visit Windows

The Baseline value is defined as the most recent non-missing value collected prior to the administration of the first dose.

Efficacy, safety and PK assessments will be summarized by analysis visits as presented in Table 1 below.

Table 1 Analysis Visit Windows

Analysis Visit Name	Target Study Day	Study Day Interval
Baseline	1	≤1
Week 1	8	2 to 11
Week 2	15	12 to 18
Week 3	22	19 to 25
Week 4	29	26 to 32
Week 5	36	33 to 39
Week 6	43	≥40

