5.3.3 Unscheduled Assessments

Both scheduled and unscheduled assessments, including early termination visits, will be considered for planned timepoint analyses based on the above analysis visit windowing rules. All assessments will be presented in data listings.

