5.3.4 Multiple Measurements within Visit Windows

If multiple non-missing continuous measurements exist in an analysis window, the measurements will be selected based on the following rules if a single value is needed:

- For Baseline visit, the assessment closest to and prior to the time of the first dose, whether scheduled or unscheduled, will be used as the baseline value. If multiple measurements occur on the same day at the same time or the time is not available, the one with later nominal visit (scheduled visits take precedence over unscheduled visit) will be selected.
- For post-baseline visits, the assessment closest to the target study day will be selected for the by-visit analyses. In these analyses, if two assessments are equidistant from the target day then the chronologically last assessment will be used. If two assessments have the same date/time, the one with later nominal visit (scheduled visits take precedence over unscheduled visit) will be selected.

If multiple non-missing categorical measurements exist in an analysis window, the measurements will be selected based on the following rules if a single value is needed:

- For Baseline visit, the assessment closest to and prior to the time of the first dose, whether scheduled or unscheduled, will be used as the baseline value. If multiple measurements occur on the same day at the same time or the time is not available, the value with the lowest severity will be selected.
- For post-baseline visits, the assessment closest to the target study day will be selected for
 the by-visit analyses. In these analyses, if two assessments are equidistant from the target
 day then the chronologically last assessment will be used. Exceptions may be made for
 incomplete assessments, in which case, more complete assessments may be given
 priority. If multiple measurements occur on the same day, the value with the highest
 severity will be selected.

For safety analysis where the most extreme values should be selected (e.g. overall post-baseline minimum, overall post-baseline maximum, and potentially clinically important values), all non-missing post-baseline values should be considered, regardless of whether the value is selected for the by-visit summaries. All results will be presented in data listings.

When ECG is collected in triplicate, the average of the triplicate will be considered as one assessment for the analyses.

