13.2 Secondary and Exploratory Efficacy Analyses

The change from Baseline at each post-baseline timepoint in the ABC subscale scores (lethargy, stereotypic behavior, hyperactivity, inappropriate speech), the CGI-S of irritability score and the CGI-I of irritability score will be analyzed using an MMRM model similar to the primary analysis described above for the primary endpoint, except that the Baseline covariate of the endpoint being analyzed will be included in the model instead of the Baseline ABC-I subscale score. For CGI-I of irritability score, the Baseline covariate include in the MMRM model will be the Baseline CGI-S of irritability score

The change from Baseline at each post-baseline timepoint in the RBS-R scores, the VABS-Socialization subscale score, and the CGSQ scores will be analyzed using an MMRM model similar to the primary analysis described above for the primary endpoint, except that the Baseline value of the endpoint being analyzed will be included in the model instead of the Baseline ABC-I subscale score, also the visit variable included in the model will reflect the visits scheduled for the respective endpoints.

The proportion of subjects with ≥25% reduction in the ABC-I subscale score, the proportion of subjects with a CGI-I of irritability score of 1 or 2, and the proportion of subjects with ≥25% reduction in the ABC-I subscale score and a CGI-I of irritability score of 1 or 2 will be summarized at each post-Baseline timepoint. The proportions will be compared between each pimavanserin dose group and the placebo group using Cochran-Mantel-Haenszel test stratified by age group and region; Newcombe's 95% CI stratified by age group and region will be presented. Subjects with missing score at a given visit are considered as non-responders for that visit.

In addition to the treatment comparisons for the Week 6 timepoint, the treatment groups will also be compared at each of the other timepoints (Weeks 1, 2, 3, 4, or 5). These comparisons will be considered exploratory.

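### Weekly analysis windows leave many early-termination RBS-R, VABS-Socialization and CGSQ scores outside their own models; endpoint-specific windows would recover part of them

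*SAP*

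**What the plan says.** SAP 5.3.2 has a single window table: "Efficacy, safety and PK assessments will be summarized by analysis visits as presented in Table 1 below". After baseline it gives Week 1 = Days 2-11, Week 2 = Days 12-18, Week 3 = Days 19-25, Week 4 = Days 26-32, Week 5 = Days 33-39 and Week 6 = Day 40 or later.

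SAP 5.3.3 places ET visits by the same table: "Both scheduled and unscheduled assessments, including early termination visits, will be considered for planned timepoint analyses based on the above analysis visit windowing rules".

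Within a window, SAP 5.3.4 selects by distance: "For post-baseline visits, the assessment closest to the target study day will be selected for the by-visit analyses".

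Three secondary scales are not weekly:
- RBS-R (SAP 5.2.4): "The RBS-R will be administered at Screening and Baseline, and at the Week 3 and Week 6 visits".
- VABS-Socialization (SAP 5.2.5): "The VABS-Socialization will be administered at Baseline and at the Week 3 and Week 6 visits".
- CGSQ (SAP 5.2.6): "The CGSQ will be administered at Screening and Baseline, and at the Week 2, Week 4, and Week 6 visits".

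For their MMRMs, SAP 13.2 says that "the visit variable included in the model will reflect the visits scheduled for the respective endpoints".

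All three scales are marked in the EOT/ET column of the schedule (Protocol Table S-1, SAP Appendix 21.1). Protocol 4.5.1 asks sites to make reasonable efforts to complete that visit when a subject stops early.

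**The concern.** These provisions do not fit together for the three sparse scales. A subject who stops on Day 15 completes an RBS-R at the ET visit. Table 1 labels that score Week 2, and the RBS-R model has no Week 2. Neither document gives wider windows for these scales or moves an ET score to a scheduled visit. The SAP never says outright that such scores are left out; it follows from reading 5.3.2, 5.3.3 and 13.2 together.

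At stake is the use of data that families have already provided. A subject can be in the Full Analysis Set through a post-baseline ABC-I score and still contribute nothing after baseline to these models. The missing-at-random assumption is easier to defend when the last score before dropout is in the model.

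**Working it through.** **Inputs.** Windows from SAP Table 1; modelled visits from SAP 5.2.4-5.2.6 and 13.2; sample size from SAP 3.5. The documents give no distribution of discontinuation times, so timing is an assumption throughout. The base case is uniform over Days 2-39 (38 days), because from Day 40 an ET score counts as Week 6.

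**The plan's own figure.** Difference 5, SD 10, two-sided 0.05, 80% power: the t-test solution is 63.8, so 64 per arm (power 0.801). 64 / 0.85 = 75.3, so 76 per arm and 228 in total. This reproduces the plan. Planned discontinuations per arm: 76 - 64 = 12.

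**ET days that map to no modelled visit.**
- RBS-R/VABS: only Days 19-25 map to a model visit. Days 2-18 (17) and 26-39 (14) do not: 31/38 = 82%.
- CGSQ: Days 12-18 and 26-32 map. Days 2-11 (10), 19-25 (7) and 33-39 (7) do not: 24/38 = 63%.
- Under other timings tried (weights halving every 10 days, weights doubling every 10 days, ET only on nominal visit days) the shares are 80-87% and 60-71%.

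**Subjects with no modelled post-baseline value.** This is a smaller group, because later dropouts usually have a scheduled score already.
- RBS-R/VABS, ET on Days 2-18: 17/38 = 45%; 12 x 17/38 = 5.4 per arm.
- CGSQ, ET on Days 2-11: 10/38 = 26%; 12 x 10/38 = 3.2 per arm.
- Sensitivity to timing: with weights halving every 10 days the shares are 75% and 54% (12 x 0.746 = 8.9 and 12 x 0.539 = 6.5). With weights doubling every 10 days they are 17% and 8% (12 x 0.174 = 2.1 and 12 x 0.077 = 0.9).

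**Effect of endpoint-specific windows.** Take RBS-R/VABS Week 3 = Days 2-39, CGSQ Week 2 = Days 2-22 and CGSQ Week 4 = Days 23-39. Assume scheduled visits fall on target (Days 15, 22, 29) and apply the closest-to-target rule.
- RBS-R/VABS now: Days 19-22 used, 4/38. After: Days 2-22, 21/38.
- CGSQ now: Days 12-15 and 26-29, 4 + 4 = 8/38. After: Days 2-15 and 23-29, 14 + 7 = 21/38.
- Still unused after the change: 17/38 (45%) for each. These scores follow an on-time scheduled value in the same window.

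**Size of the gain in precision (illustration).** Assume 64 completers per arm, monotone missingness and a Week 3-Week 6 correlation r of 0.5 to 0.7. With m dropouts who have only a Week 3 value, the variance of the Week 6 mean is proportional to 1 - r^2 x m/(64 + m). The change raises m from 7 (12 - 5) to 12.
- r = 0.5: 0.9754 to 0.9605; the SE falls by 1 - sqrt(0.9605/0.9754) = 0.8%.
- r = 0.7: 0.9517 to 0.9226; the SE falls by 1.5%.

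**The case against.** The strongest case against acting is that narrow windows around target days are a legitimate choice. RBS-R asks about the previous month, so a score in the first days of treatment mostly describes behaviour before treatment, and labelling it Week 3 is a stretch. The gain in precision is about 1%. The three scales carry no formal inference under SAP 12.4, and the addendum confines the testing procedure to the primary endpoint. All of this stands, and it limits the point to a cheap improvement.

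A reader might also infer more than the documents support:
- *That about 10 (12 x 31/38) and 8 (12 x 24/38) subjects per arm are lost.* Those are unused scores. Many of these subjects already have a scheduled score in the model.
- *That anyone who stops before the Week 3 window contributes nothing to any of the three scales.* This is wrong for CGSQ, where an ET score on Days 12-18 counts as Week 2.
- *That SAP 5.3.3 promises to use ET scores and is contradicted.* It says they are considered under the windowing rules, which is compatible with some falling outside a model visit.
- *That wider windows would recover everything.* An ET RBS-R on Day 30 stays unused if a Day 22 score exists.
- *That laboratory and ECG tables need the same change.* Under SAP 5.3.4, safety extremes and potentially clinically important values already draw on all post-baseline results.

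**Conclusion.** The mismatch is real and limited. ET scores on Days 2-18 or 26-39 (RBS-R, VABS-Socialization) and on Days 2-11, 19-25 or 33-39 (CGSQ) are listed but do not enter the MMRM. Under uniform timing, at most about 5 subjects per arm have no modelled RBS-R/VABS value and about 3 have no modelled CGSQ value for this reason.

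Given that timing, these counts are upper bounds. The 15% discontinuation rate is a ceiling, no ET visit takes place after full withdrawal of consent, and none is expected after loss to follow-up or death. The timing itself is not known: dropout concentrated in the first weeks would raise the shares, and later dropout would lower them.

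The primary endpoint, CGI-S and CGI-I are scheduled every week, so their ET scores always map to a modelled visit.

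**What to change.** Add endpoint-specific windows to SAP 5.3.2 and leave Week 6 (Day 40 or later) as it is. For example:
- RBS-R and VABS-Socialization: Week 3 = Days 2-39.
- CGSQ: Week 2 = Days 2-22; Week 4 = Days 23-39.

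Keep the closest-to-target rule of SAP 5.3.4, so that an on-time scheduled score still takes precedence over a more distant ET score. Every subject with an ET score and no other modelled value then gains one, and no score from before Day 40 enters the Week 6 endpoint. If the sponsor prefers to keep narrow windows, the SAP should say that off-schedule ET scores on these scales are listed only.

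The cost is one table edit and some programming. The downside is that some values will lie far from their target day, most of all very early RBS-R scores given the one-month recall. Laboratory and ECG tables need no change.

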5.3.3 Unscheduled Assessments

Both scheduled and unscheduled assessments, including early termination visits, will be considered for planned timepoint analyses based on the above analysis visit windowing rules. All assessments will be presented in data listings.

5.3.4 Multiple Measurements within Visit Windows

If multiple non-missing continuous measurements exist in an analysis window, the measurements will be selected based on the following rules if a single value is needed:

- For Baseline visit, the assessment closest to and prior to the time of the first dose, whether scheduled or unscheduled, will be used as the baseline value. If multiple measurements occur on the same day at the same time or the time is not available, the one with later nominal visit (scheduled visits take precedence over unscheduled visit) will be selected.
- For post-baseline visits, the assessment closest to the target study day will be selected for the by-visit analyses. In these analyses, if two assessments are equidistant from the target day then the chronologically last assessment will be used. If two assessments have the same date/time, the one with later nominal visit (scheduled visits take precedence over unscheduled visit) will be selected.

If multiple non-missing categorical measurements exist in an analysis window, the measurements will be selected based on the following rules if a single value is needed:

- For Baseline visit, the assessment closest to and prior to the time of the first dose, whether scheduled or unscheduled, will be used as the baseline value. If multiple measurements occur on the same day at the same time or the time is not available, the value with the lowest severity will be selected.
- For post-baseline visits, the assessment closest to the target study day will be selected for
 the by-visit analyses. In these analyses, if two assessments are equidistant from the target
 day then the chronologically last assessment will be used. Exceptions may be made for
 incomplete assessments, in which case, more complete assessments may be given
 priority. If multiple measurements occur on the same day, the value with the highest
 severity will be selected.

For safety analysis where the most extreme values should be selected (e.g. overall post-baseline minimum, overall post-baseline maximum, and potentially clinically important values), all non-missing post-baseline values should be considered, regardless of whether the value is selected for the by-visit summaries. All results will be presented in data listings.

When ECG is collected in triplicate, the average of the triplicate will be considered as one assessment for the analyses.

